We do not foresee missing data being a problem as when we design measures in Qualtrics all fields will require a response, and all data will be collected by a researcher during the restaurant visit. However, it is possible that some participants will not complete the online questionnaire to assess later intake after the restaurant visit. Any missing data for later nutrient intake will be imputed.

Multiple comparisons

The alpha will be set at .05 for primary and secondary outcome analyses. To adjust for multiple comparisons, the alpha for exploratory analyses alpha will be reduced to .01.

Sample size

The label in the present study (or a similar label) has not previously been tested in a real-world UK context, in terms of PME or food choice. A RCT examining the effects of 'high in' added sugar labels on PME found large effects ($d = 0.58 - 0.63$) (7). A meta-analysis on food labelling found a small effect ($OR = 0.65$, or $d = .24$) of warning labels in terms of reducing consumers' probability of selecting less healthy items (31). However, a RCT examining the effects of 'high in' sodium labels on salt (g) and 'high in' item choice found very small effects ($d = 0.03$ and 0.04 respectively) (9), but there are important methodological differences (e.g., menu size) between this study and the present study. The primary purpose of the present study is to examine PME, so we will therefore power the study for this primary outcome, but in doing so we will have reasonable power to detect small-medium effects for our secondary outcome (food choice).

In the present study, G power calculation indicates a minimum sample of 260 participants (130 per condition) will provide sufficient power (80%, two-tailed) to detect small-medium between condition effects ($d = 0.35$) of the salt warning label on PME, salt purchased, and salt intake using between-subject ANOVAs (as planned).

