Prior to the study we do not know with certainty what the rate of participant recruitment will be, and effect size estimates have a degree of uncertainty. To balance the trade-off between costs (e.g., in research time, participant burden) and likelihood of the study providing convincing evidence, we will conduct interim analyses. When we have collected data for 260 participants (130 completers in each condition), we will conduct interim analyses to assess whether the results are convincing enough to conclude that an effect on PME and odds of selecting a high salt meal are present or absent (32). The interim analyses will examine the effect size estimates of these two outcomes and current statistical significance. If it is extremely unlikely that either of the predicted effects would be observed up to maximum sample size capacity ($n = \sim 500$) based on time and resource constraints, then we will cease data collection at this point and conduct planned analyses. However, if the

observed effect size suggests that a detectable effect ($d \geq 0.25$) is present but is not statistically significant, data collection will continue and we will attempt to recruit the largest possible sample size up until the end of September 2024 at the latest. In this scenario, consistent with best practice recommendations for interim analyses and to account for multiple testing, the p value for these outcomes will be adjusted to 0.025.

References

2. Salt Ao. Salt and Your Health 2023 [Available from: <https://www.actiononsalt.org.uk/salthealth/>].
3. BHF. Reducing the UK's salt intake: potential benefits 2022 [Available from: <https://www.bhf.org.uk/what-we-do/policy-and-public-affairs/creating-healthier-environments/reducing-the-uks-salt-intake#:~:text=On%20average%20the%20UK%20population,Health%20Organization's%20recommendation%20of%205g.>].
5. Interest CfSITP. NYC Mayor Eric Adams signs Sweet Truth Act 2023 [Available from: <https://www.cspinet.org/press-release/nyc-mayor-eric-adams-signs-sweet-truth-act>].

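### At 130 per arm and alpha .05, the interim rule for continuing recruitment can never be met for PME in the default regression, and some non-significant results fall under neither the stop rule nor the continue rule.

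*Combined protocol and SAP*

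**What the plan says.** The Sample size section gives 260 participants (130 per condition) for 80% two-sided power at d = 0.35, and says that PME is the outcome the study is powered for. Under Multiple comparisons, "The alpha will be set at .05 for primary and secondary outcome analyses". The Statistical analysis section analyses PME by individual-level linear regression. It moves to a mixed model with table as a random effect only if a likelihood ratio test for clustering is significant.

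The last paragraph of the Sample size section sets an interim look at 130 completers per condition, covering PME and the odds of choosing a high-salt meal. It contains two rules:

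- **Stop:** "If it is extremely unlikely that either of the predicted effects would be observed up to maximum sample size capacity" (about 500), data collection ends. No probability is attached to this.
- **Continue:** if the "observed effect size suggests that a detectable effect ($d \geq 0.25$) is present but is not statistically significant", the team will "attempt to recruit the largest possible sample size up until the end of September 2024 at the latest".

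The adjusted level follows the continue rule: "In this scenario, consistent with best practice recommendations for interim analyses" and to allow for multiple testing, "the p value for these outcomes will be adjusted to 0.025". No separate level is stated for the first look.

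**The concern.** A continue rule has to cover results that are promising but not yet significant. Here the effect-size threshold (0.25) lies just above the smallest d that is significant at .05 with 130 per arm. For PME in the default model, any result large enough to qualify is therefore already significant, and no result can meet both conditions. The cause is a mismatch: .025 applies only after the decision to continue, so the threshold is set against a first look that is still tested at .05.

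The two rules also do not meet. A non-significant result below 0.25 does not qualify to continue, and unless success is judged extremely unlikely it does not qualify to stop. Because that judgement has no number, the decision on a near miss would be made after the interim results have been seen.

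**Working it through.** **Inputs.** From the documents: 130 per arm, two-sided .05, d = 0.35, 80% power, trigger d ≥ 0.25, .025 after continuing, maximum n about 500. Assumed, because the documents do not give them: design effect, table sizes, control choice rate, and the final n actually reached.

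**1. The plan's own figure.** Noncentral t with 130 per arm, d = 0.35 and alpha .05 gives power 80.3%. The 260 reproduces.

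**2. Smallest significant d at the interim.** Critical d = t(1 − α/2, 258) × √(2/130):

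| Level | t | Critical d |
|---|---|---|
| .05 | 1.969 | 0.244 |
| .0294 | 2.190 | 0.272 |
| .025 | 2.255 | 0.280 |

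For d = 0.25, t = 0.25/√(2/130) = 2.016 and p = .045. Four covariates (254 df) leave the .05 value at 0.244. At .05 the set of results with d ≥ 0.25 and p ≥ .05 is empty. At .025 it would be d = 0.25 to 0.28, holding about 9% of results if the true d is 0.25.

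**3. Where the trigger can still be met.**

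- *Mixed model.* The standard error grows with the square root of the design effect, so the window opens at (2.016/1.969)² ≈ 1.05. With tables of 4 that is an ICC of 0.048/3 = .016; with tables of 2 it is 0.048/1 = .048.
- *High-salt choice.* d = 0.25 converts to OR = exp(−0.25π/√3) = 0.635. At assumed control rates of 20 to 80%, this has p = .07 to .18 with 130 per arm, so it is non-significant and the trigger applies.

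**4. Results under neither rule.** Conditional power under the current trend, final level .025, is P(Z > (2.241 − z₁/√f)/√(1 − f)), with f = 260/n and z₁ = d/√(2/130), divided by √(design effect) where clustering is assumed:

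| Interim PME d | p (unclustered) | n = 500 | n = 400 | n = 500, design effect 1.6 |
|---|---|---|---|---|
| 0.20 | .108 | 50% | 34% | 25% |
| 0.22 | .077 | 62% | 47% | 33% |
| 0.24 | .054 | 74% | 61% | 43% |

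If success means reaching significance at the end, none of these is extremely unlikely to succeed, yet all are below 0.25.

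**5. Type I error.** With correlation √(260/500) between looks, the written rule gives 5.0 to 5.5% for PME at design effects of 1 to 1.6, and 5.2 to 5.8% for high-salt choice. The same level at both looks gives 4.2% (.025) or 5.0% (.0294).

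**6. Power at n = 260 with the adjusted level.** For d = 0.35: 71.5% (.025) or 73.6% (.0294). The d detectable with 80% power is 0.384 or 0.376.

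**The case against.** **The result for PME is conditional.** It needs a first look at .05, d and p from one estimate, and the individual-level model. The interim level is never stated, and tables are the unit of randomisation, so the mixed model may well apply. At assumed design effects of 1.2, 1.4 and 1.6, with true d of 0.25 to 0.35, the PME trigger is met in 2–4%, 8–11% and 14–15% of simulated trials when the clustering test decides the model. If a raw d were paired with a covariate-adjusted p, chance imbalance would meet it in about 2–3%. This stands. A reader might infer that the extension can never operate at all; the documents do not support that, since it remains open for high-salt choice and under the mixed model.

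**The 0.25 may be deliberate.** With 250 per arm, .05 and 80% power, the detectable d is 0.251. The protocol does not say this is where the threshold comes from, but the match is close, and it calls such an effect detectable. A reader might infer that declining to extend at d = 0.20 to 0.24 is a mistake. That does not follow, because it may be a considered trade-off against cost, which the paragraph names as its aim. What stands is only that the action for such results is not written down.

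**The futility wording has several readings.** If the predicted effect must itself be seen at n = 500, the chance from an interim d of 0.20 to 0.24 is 0.8 to 3.8% for a target of 0.35, but 21 to 44% for a target of 0.25. None of these can be taken as the plan's meaning. The spread shows why a number is needed.

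**The consequences are limited.** If the true PME effect is near the cited 0.58, only about 0.3% of unclustered trials miss significance at the interim. The study also describes itself as a pilot.

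**Conclusion.** The point holds in this limited form and should be fixed. Under the .05 stated for primary outcomes and the default regression, the continue rule is empty for PME; that follows from the plan's own figures alone. At the design value d = 0.35, about 20% of unclustered trials (100 − 80.3) miss significance at 260, and none could continue on the strength of PME. The gap between the rules is a real omission, but its size rests on the assumed final n and design effect and on reading success as final significance.

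A reader might also infer a serious inflation of type I error. The calculations do not bear that out: about 5.0 to 5.8%, and 6.4% even if every non-significant result continued. The fault is that the threshold and the first-look level do not match, and that the decision rule is incomplete.

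**What to change.** Rewrite the interim paragraph.

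- **(a) One level at both looks.** Test PME and high-salt choice at the same pre-set level at the interim and at the end, whether or not recruitment continues: the plan's .025 (overall error about 4.2%) or .0294 (about 5.0%).
- **(b) Complementary rules.** Define what counts as success and give the futility wording a pre-set number, computed with the analysis model including table. State the action for a non-significant d below 0.25. The cut-off is the sponsor's choice. Keeping 0.25 as the smallest effect worth pursuing is acceptable; at .025 the unclustered PME continuation window is then d = 0.25 to 0.28.
- **(c) Restated power.** For d = 0.35 at n = 260, give about 71.5% (.025) or 74% (.0294), or give the detectable d as 0.384 or 0.376.

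**Cost.** One paragraph, and 7 to 9 points of power at n = 260 (80.3% to 73.6% or 71.5%). Depending on the cut-off, more trials continue. With an illustrative 20% conditional-power cut-off at .0294 and true d = 0.35, about 22% continue unclustered and about 34% at a design effect of 1.6. Overall power is then 93% against 80% as written if 500 is reached unclustered, but only 68% against 67% if 350 is reached at a design effect of 1.6. Any gain depends on the final n and on clustering, neither of which the documents give.

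### The alpha cut to .025 applies only after the study continues past the look at 260, so it does not guarantee 5% error for PME or high-salt meal choice

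*Combined protocol and SAP*

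**What the plan says.** The Multiple comparisons section sets the general level: "The alpha will be set at .05 for primary and secondary outcome analyses".

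The Sample size section then adds a look: "When we have collected data for 260 participants (130 completers in each condition), we will conduct interim analyses". Its purpose is "to conclude that an effect on PME and odds of selecting a high salt meal are present or absent". On how this is judged, it says: "The interim analyses will examine the effect size estimates of these two outcomes and current statistical significance". No numerical threshold for that look is given.

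Two outcomes of the look are described. Recruitment stops if a predicted effect looks very improbable by the maximum of about 500. If the observed d is at least 0.25, so that an effect "is present but is not statistically significant, data collection will continue", recruitment goes on until the end of September 2024 at the latest. Only in that second case does the plan say "the p value for these outcomes will be adjusted to 0.025", and it presents this as the allowance for multiple testing.

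**The concern.** Total type I error over two looks is the first-look error plus the chance of rejecting at the second look after not rejecting at the first. If the first look is judged at .05, the first term alone is 5%, and any positive second term takes the total above it. A reduction that starts only at the second look makes the excess smaller but cannot remove it.

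At stake is the claim on PME, the outcome that the study is powered for, and on high-salt meal choice. An interim p between .025 and .05 would be reported as a finding although a second chance had been built in. The step described as correcting for this would never have applied to it.

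A related point is the d of 0.25 called detectable. It matches 80% power at about 500 and alpha .05, not the .025 imposed in the same paragraph.

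**Working it through.** **Inputs from the plan.** Interim n = 260 (130 per condition); maximum about 500 (250 per condition assumed); two-sided tests; 80% power; design d = 0.35; continuation trigger d = 0.25; alpha .05 in general and .025 after continuing. The .05 at the interim is inferred. Figures are per outcome and at individual level unless a design effect is stated.

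**1. The plan's own sample size.** n per arm = 2(1.960 + 0.842)²/0.35² gives 129 by the normal formula. The t-based solution is 129.1, so 130 per arm and 260 in total, with power 80.3%. The stated 260 is reproduced at alpha .05.

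**2. Two-look error.** The interim and final z are bivariate normal with correlation ρ = √(260/500) = 0.721. With critical values c1 and c2 and a lower continuation limit l on |Z1|,

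total = α1 + 2∫ from l to c1 of φ(x)·[P(Z2 > c2 | x) + P(Z2 < −c2 | x)] dx.

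With l = 0 (every non-significant interim continues):

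| Interim / final level | Final N | Total error |
|---|---|---|
| .05 / .025 | 300 | 5.4% |
| .05 / .025 | 400 | 6.1% |
| .05 / .025 | 500 | 6.4% |
| .025 / .025 | 500 | 4.25% |
| .0294 / .0294 | 500 | 4.96% |

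The equal level that spends exactly 5% at 260/500 is about .0296.

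**3. The trigger as written, PME.** At 130 per arm, d = 0.25 gives t = 0.25/√(2/130) = 2.016, p = .045. The critical d at .05 is 0.244. Every d of 0.25 or more is therefore already significant, the continuation window is empty, and error on PME's own trigger is 5.0%.

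Tables are the unit of randomisation, and the plan provides a mixed model if clustering is detected. With an assumed design effect DE, z at the trigger is 0.25/√(4·DE/260):

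- DE 1.25: z = 1.80, error 5.2%
- DE 1.5: z = 1.65, error 5.4%
- DE 2.0: z = 1.43, error 5.7%

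**4. The trigger as written, meal choice.** Convert d to a log odds ratio: 0.25 × π/√3 = 0.453 (OR 1.57, or 0.64 in the other direction). The null standard error is √(2/[130·p(1−p)]), where p is an assumed selection rate.

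- p = .5: z = 1.83, p-value .068, error 5.2%
- p = .4: z = 1.79, p-value .073, error 5.2%
- p = .3: z = 1.68, p-value .094, error 5.4%

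Here the window exists, because d = 0.25 is not yet significant at 260.

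**5. The d called detectable.** At 250 per arm, (z for α/2 + 0.842) × √(2/250) gives 0.251 at .05 and 0.276 at .025. Power for d = 0.25 is 79.7% at .05 and 70.8% at .025. Reaching 80% at .025 would need about 305 per arm, roughly 610 in total, which exceeds the stated capacity.

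**The case against.** The strongest reply is that the plan does not continue after every non-significant interim. It continues only for d of at least 0.25, and under that rule PME shows no excess without clustering and meal choice only 0.2-0.4 percentage points. If continuation happens only in the predicted direction, meal choice is at 5.1-5.2%. In a study that calls itself a pilot, that is little. This stands, and it is why 6.4% is given only as an upper bound. The bound still matters, because the plan does not say what happens when d is below 0.25 but an effect is not hopeless, or when one of the two outcomes is significant and the other is not. Continuation in practice could be wider than the written trigger.

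A second reply is that .025 may have been meant at both looks, which gives 4.25%. The text does not say so, since it ties the reduction to continuing. If that was the intention, the same change of wording settles it.

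A reader might also infer that salt purchased and salt intake need the same correction because they stay at .05. The documents do not support this. They are not interim outcomes and are tested once, so there is no repeated look at them. Inflation could come only through correlation with meal choice. In simulation under the written trigger (selection rate 50%), their error was 4.9%, 4.9% and 4.8% at assumed correlations of 0.5, 0.8 and 0.95. It rises to 5.3%, 6.0% and 7.0% only if every non-significant interim continues, which is not the written rule.

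Finally, the plan does not say how 0.25 was derived. That it is an alpha .05 figure is an inference from the arithmetic.

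**Conclusion.** The concern holds in a limited form. As worded, the correction does not guarantee 5% two-sided error for PME or high-salt meal choice, because the first look appears to be at .05 and only the second is reduced. The size is modest:

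- meal choice: about 5.2-5.4% under the written trigger, assuming selection rates of 30-50%;
- PME: 5.0% on its own trigger without clustering, and about 5.2-5.7% under assumed design effects of 1.25-2.0;
- either outcome: at most 6.4% at about 500.

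It would be wrong to read this as showing that the plan exceeds 5% for every outcome, or that 6.4% is its error rate as written. The conclusion rests on the inferred .05 at the interim and on a maximum near 500. The point should be corrected because the step is presented as controlling multiplicity and, as written, does not.

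**What to change.** In the Sample size section, state one nominal two-sided level that applies to PME and high-salt meal choice at both the look at 260 and the final analysis: .025 at each look (4.25% in total at 260/500), or .0294 at each (Pocock, 4.96%). Either keeps the total within 5% per outcome whatever the continuation rule turns out to be, up to about 500. Add a cross-reference in the Multiple comparisons section, so that the general .05 is not read as the interim level. Note beside the 0.25 trigger that at .025 and about 500 the effect detectable with 80% power is d of about 0.28, and that power for 0.25 is 71% (individual-level figures).

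A lower interim level also gives PME a usable continuation window. The critical d at 260 becomes 0.280 at .025 or 0.272 at .0294, so a d of 0.25 is no longer already significant.

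The change is to wording only. Its cost is power at the first look: for d = 0.35 at 260 it falls from 80.3% to 71.5% (.025) or 73.6% (.0294). Recruitment beyond 260 therefore becomes more likely. No change is needed for salt purchased or salt intake on this account.

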Appendix A – Screening questionnaire

Where do you live?

- In the United Kingdom (1)
- In a different country (2)

Are you fluent in English?

- Yes (1)
- No (2)

What is your age (in years)?

What is your sex? A question about gender identity will follow.

- Male (1)
- Female (2)

Which of the following best describes your gender?

- Man (1)
- Non-binary (2)
- Woman (3)
- Prefer to self-describe (4)
- Prefer not to say (5)

Are you a University student?

- Yes (2)
- No (3)

What is your highest educational qualification? If you are a student, please select the qualification being studied for.

- Less than high school (no formal qualifications) (1)
- High school completion (e.g., GCSEs or equivalent) (2)
- College or foundation degree (e.g., A Levels or equivalent) (3)
- Bachelor's degree (4)
- Master's degree (5)
- Doctorate or professional degree (6)

Do you have any dietary allergies?

Yes (please describe) (1) _____

No (2)

Do you have any dietary requirements?

No (1)

Vegetarian (2)

Vegan (3)

Other (please describe) (4) _____

How often, on average, over the past year have you eaten out (e.g., at a restaurant, café)?

Not in the last year (1)

Less than once per month (2)

1 - 3 times per month (3)

1 - 2 times per week (4)

3 times per week or more (5)

Please provide your email address so that the researcher can contact you:
Make sure there are no typos in your email address.

Appendix D – Order form

ORDER FORM

Booking Name: University of Liverpool

Table Number:

Group size:

STUDY ID	INITIALS	EMAIL ADDRESS	MEAL	DRINK

Appendix E – Post-exposure assessments

Please enter your participant ID. If you are unsure what this is, please ask the researcher.

Please select the letter which is circled on your sticker label. If you are unsure, please ask the researcher.

A (1)

B (2)

End of Block: Default Question Block

Start of Block: Aim guessing

What do you think was the aim of this study?

End of Block: Aim guessing

Start of Block: Food sharing

Did you share any of the food or drink items?

Yes (1)

No (2)

Display This Question:

If Did you share any of the food or drink items? = Yes

What items were shared? Please also give an estimation in % of how much of each item was shared.

Did you add any condiments (e.g., sauce, salt) to your food?

- Yes (1)
- No (2)

Display This Question:

If Did you add any condiments (e.g., sauce, salt) to your food? = Yes

What condiments did you add? Please also give an estimation in teaspoons of how much of each condiment was added.

End of Block: Food sharing

Start of Block: PME

Please consider the following statements in relation to the menu you ordered from.

Not at all (1) A little bit (2) Somewhat (3) Quite a bit (4) A great deal (5)

The menu made me concerned about the health effects of consuming items high in salt. (1)

The menu
made
consuming
items high in
salt seem
unpleasant. (2)

The menu
discouraged
me from
wanting to
consume
items high in
salt. (3)

 End of Block: PME**Start of Block: Attention check**

This question is an attention check, so please answer truthfully. How many times have you visited the planet Mars?

- Several times (1)
- Just once (2)
- Never (3)

End of Block: Attention check**Start of Block: Awareness**

Did you notice any warning labels next to any of the menu items when making your meal selection?

- Yes (1)
- No (2)

Display This Question:

If Did you notice any warning labels next to any of the menu items when making your meal selection?

= Yes

What did the label tell you about?

Healthy items (1)

Organic (2)

Calcium (3)

Sustainable (4)

Added sugars (5)

Vegetarian (6)

Unhealthy items (7)

Salt (8)

Fibre (9)

Gluten free (10)

None of these (11)

Not sure (12)

Display This Question:

If Did you notice any warning labels next to any of the menu items when making your meal selection?

= Yes

Please describe what the warning label said.

Page Break

Did you think about the salt content of the meals when making your selection?

Yes (1)

No (2)

End of Block: Awareness

Start of Block: Additional assessments

Display This Question:

If Please select the letter which is circled on your sticker label. If you are unsure, please ask th... = B

Here is the menu you ordered from. The menu features salt warning labels next to items that exceed 50% of the daily recommended limit for salt intake: [menu B image]

Display This Question:

If Please select the letter which is circled on your sticker label. If you are unsure, please ask th... = A

Here is a slightly different version of the menu you ordered from. The menu features salt warning labels next to items that exceed 50% of the daily recommended limit for salt intake: [menu B image]

Did you learn something new from the salt labels on the menu?

Yes (1)

No (2)

Display This Question:

If Please select the letter which is circled on your sticker label. If you are unsure, please ask th... = B

Did the salt labels influence which food you ordered from the menu?

Yes (1)

No (2)

Display This Question:

If Did the salt labels influence which food you ordered from the menu? = Yes

How did the salt label influence your choice?

I avoided choosing a meal high in salt (1)

I chose a meal high in salt (2)

Other (please describe) (3) _____

Display This Question:

If Please select the letter which is circled on your sticker label. If you are unsure, please ask th... = A

Would the salt labels have influenced which food you ordered from the menu?

Yes (1)

No (2)

Display This Question:

If Would the salt labels have influenced which food you ordered from the menu? = Yes

How would the salt labels have influenced your choice?

- I would have avoided choosing a meal high in salt (1)
- I would have chosen a meal high in salt (2)
- Other (please describe) (3) _____

If the UK Government introduced policy requiring restaurant menu items high in salt to feature these labels, how would you feel?

- Strongly oppose (1)
- Oppose (3)
- Neutral (4)
- Support (5)
- Strongly support (6)

Please use this box to add any additional thoughts which you may have about the salt label.

End of Block: Additional assessments

Start of Block: Demographics

What is your age (in years)?

What is your sex? A question about gender identity will follow.

- Male (1)
- Female (2)

Which of the following best describes your gender?

- Man (1)
- Non-binary (2)
- Woman (3)
- Prefer to self-describe (4) _____
- Prefer not to say (5)

What is your highest educational qualification? If you are a student, please select the qualification being studied for.

- Less than high school (no formal qualifications) (1)
- High school completion (e.g., GCSEs or equivalent) (2)
- College or foundation degree (e.g., A Levels or equivalent) (3)
- Bachelor's degree (4)

- Master's degree (5)
- Doctorate or professional degree (6)

What is your current employment status?

- Full-time (1)
- Part-time (2)
- Student (3)
- Retired (4)
- Unable to work due to sickness/disability (5)
- Looking after home/family (6)
- Unemployed (7)
- Other (please describe) (8) _____

What is your ethnic group? Choose one option that best describes your ethnic group or background.

- Asian or Asian British** Bangladeshi Chinese Indian Pakistani Any other Asian background (3)
- Black, Black British, Caribbean or African** African Caribbean Any other Black, Black British, or Caribbean background (5)
- Mixed or multiple ethnic groups** White and Black Caribbean White and Asian White and Black African Any other Mixed or multiple ethnic background (6)
- White** English, Welsh, Scottish, Northern Irish or British Irish Gypsy or Irish Traveller Roma Any other White background (7)

Other ethnic group Arab Any other ethnic group (8)

What is your height?

In centimetres: (1) _____

OR in feet and inches: (2) _____

Prefer not to say (4)

What is your weight?

In kilograms: (1) _____

OR in stone and pounds: (2) _____

Prefer not to say (4)

How often, on average, over the past year have you eaten out (e.g., at a restaurant, café)?

Not in the last year (1)

Less than once per month (2)

1 - 3 times per month (3)

1 - 2 times per week (4)

3 times per week or more (5)

End of Block: Demographics

Start of Block: Health motives

Several different factors influence our choice of food. Read each item carefully and decide how important the item is to you. There are no right or wrong answers, we are interested in what is important to you. It is important to me that the food I eat on a typical day...

	Not at all important (1)	A little important (2)	Moderately important (3)	Very important (4)
Contains a lot of vitamins and minerals (1)				
Keeps me healthy (2)				
Is nutritious (3)				
Is high in protein (4)				
Is good for my skin/teeth/hair/nails etc. (5)				
Is high in fibre and roughage (6)				

